# Table 8: Secondary outcome measures

Соногт	SECONDARY OUTCOME MEASURE	
	Thrombotic events	
	Diagnosis of venous thromboembolism	
	Diabetes and associated complications	
	Diagnosis of diabetes or associated complications (including retinopathy,	
	impaired renal function)	
	Second malignancies	
	Diagnosis of a new primary cancer	
	Age-related macular degeneration (AMD)	
	Diagnosis of AMD	
	Cognitive assessment	
	Using the Montreal Cognitive Assessment (MoCA-Blind)	
	Dementia	
	Diagnosis of dementia (of any type), reported by sub-type	
	Functional capacity	
	Using the VES-13 questionnaire	
	Exercise levels	
	Measured using the International Physical Activity Questionnaire (IPAQ)	
	Long-term quality of life/late effects of cancer treatmentMeasured using	
	survivorship questionnaire	
Breast	Breast cancer-specific survival	
	Time from randomisation to breast cancer death	
	Bone metastases-free survival	
	Time from randomisation to development of bone metastasis or death	
	from any cause	
	IDFS-DCIS	
	Defined as for IDFS except that ductal carcinoma in situ (DCIS) (ipsilateral	
	or contralateral) is additionally included as an event 	
Colorectal	Colorectal cancer-specific survival	
	Time from randomisation to colorectal cancer death	
Gastro-oesophageal	Disease-free survival	
	Time from randomisation to disease recurrence or death from any cause	
Prostate	Prostate cancer-specific survival (PCSS)	
	Time from randomisation to prostate cancer death	
	Time to initiation of salvage treatment	
	Time from randomisation to initiation of salvage treatment	
	Bone metastases-free survival	
	Time from randomisation to development of bone metastasis or death	
	from any cause	

# **10.3 ANALYSIS METHODS**

# **10.3.1** COHORT-SPECIFIC ANALYSES OF PRIMARY OUTCOME DATA

The cohort-specific primary outcomes are all time-to-event variables with events as defined above. Participants that have not yet experienced the event in question at the time of analysis will be censored on the date they were last known to be event-free.

At the time the trial was designed and planned, the logrank test was felt to be the most appropriate method for testing the primary hypotheses and so each of the cohorts has been powered on this

basis. However, since that time, there has been increasing evidence that the effect of aspirin on disease-related outcomes may lead to non-proportional hazards and, in particular, the possibility of a 'late effect' emerging. Since the design of the Add Aspirin trial, a number of alternative tests have been proposed which are potentially more powerful in this setting. However, as yet, an optimal or most appropriate alternative test, with fully described operating characteristics and appropriate estimates of effect, has not emerged. Nevertheless, this is a very active area of research and we expect such a test (or tests) to emerge prior to the primary analyses of the Add-Aspirin cohorts. If that is the case, the analysis plan will be updated to specify this test, rather than the logrank test, to be used to assess the primary hypotheses in Add Aspirin. This decision will be made by the Trial Steering Committee (Who remain blind to the accumulating data), rather than the Independent Data Monitoring Committee (IDMC) and will be formally updated in the analysis plan prior to analysis.

Sample size calculations for the individual cohorts are given in section 10.4. In addition to the main sample size calculations, for each cohort we have also calculated the power of the logrank test with the calculated sample size assuming a delayed effect of aspirin emerging after the first 2 years (with the mean hazard ratio from the start of the study to the time of analysis being equal to the targeted hazard ratio). This might be seen to reflect a "worst case scenario", since we would hope to identify a more powerful test for the primary analyses.

# **10.3.2** COMBINED ANALYSIS OF OVERALL SURVIVAL

The later analysis of overall survival across the cohorts combined will utilise the same methods as for the cohort-specific primary outcome data. Power calculations for this analysis are given in section 10.4. For these, we have used the joint test, stratified by cohort. This is because we anticipate that aspirin will have a late effect on overall survival, with curves separating at 3 years (and possibly beyond this). In this situation the joint test is likely to be considerably more powerful than the logrank alone. As noted above, a more optimal test may emerge over time and, in that case, the analysis plan will be updated to reflect this.

For this later analysis, data from the Add-Aspirin trial may be combined in a meta-analysis with data from other trials of aspirin in the adjuvant setting being conducted internationally. This will be dependent on the timelines for reporting each of the individual trials, and the details will be confirmed in a separate analysis plan.

# **10.3.3** SUBGROUP ANALYSES BY **PIK3CA** MUTATION STATUS

Published data from recent studies in colorectal cancer suggest that the effect of aspirin on DFS may be greater in patients who have the PIK3CA mutation than in those who do not, and in fact any effect of aspirin may be limited to this group alone. Subject to funding, this hypothesis will be formally tested in the colorectal cohort through additional comparisons which will follow the same general principles (and occur at the same time) as the primary analyses.

In order to limit the impact on the overall type I error rate of carrying out multiple significance tests, the comparisons to be performed (and their significance level) will depend on the outcome of the primary analysis as follows:

1) In the event that the primary analysis of DFS demonstrates a statistically significant effect of aspirin, two subsequent analyses will be carried out; in particular, patients with the PIK3CA mutation and those without will be analysed as separate subgroups. These analyses will be conducted at an overall 2-sided significance level of 5%. The significance level for each of the two tests will be determined by Holm's method, but will be either 2.5% or 5%. By performing this closed procedure and conditioning on obtaining a significant result in the

primary analysis, we ensure that no adjustment is needed to preserve the type I error rate for the primary analysis.

2) In the event that the primary analysis does not demonstrate a statistically significant effect of aspirin, a single subsequent analysis of only those patients with the PIK3CA mutation will be performed. A 1% 2-sided significance level will be used in order to limit the impact on the overall type I error rate for this and the primary analysis. Given that the primary analysis will be conducted using a 5% significance level, the overall type I error rate associated with performing both tests is at most 6%.

Sample size and power calculations for the subgroup analyses outlined above are given in section 10.4.6.A for the colorectal cohort.

Comparisons of aspirin vs. placebo both in patients with and without the PIK3CA mutation will form part of the planned secondary analyses in the other cohorts and shall be structured in a similar way to the colorectal cohort.

It is possible that the results of other trials investigating aspirin use in PIK3CA mutated colorectal cancer (specifically ALASCCA and SAKK 41/13) may be available prior to the primary analysis of the Add-Aspirin colorectal cohort. If this is the case, and depending on the findings from these trials, there may be an interim analysis of the Add-Aspirin data, considering the impact of PIK3CA mutation status.

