# 10.4.2 COLORECTAL COHORT

In the colorectal cohort, based on data from recent trials of adjuvant chemotherapy regimens in similar cohorts of colorectal cancer patients (specifically MOSAIC and QUASAR^109), and also considering that the Add-Aspirin cohort will be more mixed (including patients who haven't had chemotherapy and older patients), 5-year DFS in the control group is expected to be 70%. The cohort is designed to have 90% power at a 5% 2-sided significance level to demonstrate an absolute 5% improvement in this rate at 5 years (corresponding to HR=0.80).

Assuming proportional hazards, this will require 336 control arm DFS events (899 events in total) to be observed. Assuming that the cohort takes  $3^{1}/_{2}$  years to recruit, with the analysis taking place 6 years after the last randomisation, and that complete primary outcome data will not be obtainable for 10% of randomised participants by the time of analysis, the anticipated sample size needed to observe this number of events is approximately 2600 randomised participants. We expect to register at least 2890 colorectal cancer participants for the run-in period to allow for at least 10% not proceeding beyond that stage

If an effect of aspirin were not observed for the first two years, it is estimated that the power achieved by the logrank test at the time of analysis would be approximately 85% with the proposed sample size. This calculation assumes a hazard ratio of 1 (no effect) over the first two years followed

by a hazard ratio of 0.72 thereafter, which yields an estimated mean hazard ratio of 0.8 (the targeted hazard ratio for this cohort) at the time of the primary analysis of the cohort.

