#### **10.4.6** ADDITIONAL POWER CALCULATIONS FOR OTHER KEY ANALYSES

# 10.4.6.A Subgroup analyses defined by the PIK3CA mutation in the colorectal cohort

Data from recent trials indicate that the incidence of the PIK3CA mutation in patients with colorectal cancer is approximately 15%. Therefore, it is anticipated that approximately 390 of the planned 2600 patients in the Add-Aspirin colorectal cohort will have the mutation.

Depending on the outcome of the primary analysis, the significance level used in the analysis of patients with the PIK3CA mutation will be either 1%, 2.5% or 5% (see section 10.3.1). At these significance levels and with 390 patients this analysis will have 90% power to detect hazard ratios of 0.48, 0.51 or 0.54 respectively.

Under Holm's method, the significance level used in the analysis of patients without the PIK3CA mutation may be either 2.5% or 5%. With an anticipated 2210 such patients, this analysis will have 90% power to detect hazard ratios of 0.76 or 0.78 respectively.

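### The PIK3CA hypothesis is about a difference in effect between subgroups, but 10.3.3 plans only separate tests within subgroups and no comparison between them

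*Protocol*

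**What the plan says.** Section 10.3.3 starts from published data suggesting that "the effect of aspirin on DFS may be greater in patients who have the PIK3CA mutation than in those who do not", and adds that any effect may be confined to the mutated group. Subject to funding, "this hypothesis will be formally tested in the colorectal cohort through additional comparisons". The section then fixes those comparisons:

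- **Primary DFS analysis significant:** "patients with the PIK3CA mutation and those without will be analysed as separate subgroups", at an overall two-sided 5% level, with 2.5% or 5% per test under Holm's method.
- **Primary not significant:** "a single subsequent analysis of only those patients with the PIK3CA mutation will be performed", at a two-sided 1% level. The error rate for the primary plus this test is put at no more than 6%.

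The other cohorts are to follow a similar structure. Section 10.4.6.A powers only the within-subgroup tests: "it is anticipated that approximately 390 of the planned 2600 patients in the Add-Aspirin colorectal cohort will have the mutation", leaving 2,210 without it. Sections 9.2.2 and 10.8.3 also mention PIK3CA analyses, but no section names a test or estimate that compares the two subgroup effects.

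**The concern.** A claim that the effect is greater in one group than the other concerns the difference between two treatment effects. Two aspirin-versus-placebo tests, one per group, do not test that difference. When the groups differ in size by a factor of nearly six, one can be significant and the other not although the effect is identical. In the negative-primary branch no separate result for non-mutated patients is planned, so the plan would hold no evidence on whether an effect is confined to mutated tumours.

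PIK3CA status could influence who is offered aspirin. A reader given one significant and one non-significant subgroup result from what the protocol calls a formal test may conclude that the groups differ.

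**Working it through.** **Inputs from the protocol.** From 10.4.2: target HR 0.80, 5-year control DFS 70%, 899 events of which 336 are control (so 563 aspirin), recruitment over 3.5 years, analysis 6 years after the last randomisation. The design statement is "The cohort is designed to have 90% power at a 5% 2-sided significance level to demonstrate an absolute 5% improvement". From 10.4: the two aspirin arms are combined, giving 2:1. From 10.4.6.A: 15% mutated.

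**Reproducing the plan's figures.** Freedman's formula at 2:1 is (1.960 + 1.282)² × (1 + 2 × 0.80)² / [2 × (1 − 0.80)²], which gives 888 events, 1.2% below 899. With var(log HR) = 1/336 + 1/563, power at HR 0.80 is 89.9%.

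For the subgroups, control events were split 15:85 (50.4 and 285.6). Aspirin-arm events were scaled to each HR under exponential DFS with 6 to 9.5 years of follow-up.

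- Mutated: power at 0.48, 0.51 and 0.54 (1%, 2.5%, 5%) is 88.4%, 89.6% and 90.0%.
- Non-mutated: power at 0.76 and 0.78 (2.5%, 5%) is 92.0% and 91.2%.

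The stated 90% therefore reproduces to about 2 points.

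**Power in each subgroup at a uniform HR of 0.80.** Information is 1/(1/c + 1/a), with c control and a aspirin events.

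- Mutated: 50.4 and 84.45 events, information 31.6. Then 0.2231 × √31.6 = 1.25, so power is 24% at 5% and 16% at 2.5%.
- Non-mutated: 285.6 and 478.55 events, information 178.9. Then 0.2231 × √178.9 = 2.98, so power is 85% at 5% and 77% at 2.5%.

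**What the plan would show.** Subgroup log HRs were drawn 4 million times. The overall test was their information-weighted combination. Holm compared the larger |z| with 2.241, then the smaller with 1.960. Results given a significant primary:

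| Common HR | Non-mutated only | Both | Mutated only | Neither |
|---|---|---|---|---|
| 0.80 | 65% | 22% | 2% | 11% |
| 0.75 | about 61% | about 35% | 1% | 3% |
| 0.70 | about 50% | about 50% | <1% | <1% |

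At HR 0.80, non-mutated only is 73% with 10% prevalence and 57% with 20%. Of the non-mutated-only results at 15% prevalence, just 3.9% would also show an interaction with p < 0.05.

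**What an interaction test could do.** Splitting the 899 events 15:85, SE = √(1/31.6 + 1/178.9) = 0.193. The detectable ratio of HRs is exp(−2.802 × 0.193) = 0.58 at 80% power and exp(−3.242 × 0.193) = 0.53 at 90%.

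- HR 0.54 vs 1.00: 0.616/0.193 − 1.960 = 1.23, power 89%. With events scaled to those HRs, SE is 0.2035 and power 86%.
- HR 0.54 vs 0.80: 0.393/0.193 − 1.960 = 0.08, power 53%. With scaled events it is 49%.

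**Error rates under the global null.** The primary plus the 1% test gives 5.8%, inside the stated 6%. Adding a two-sided 5% interaction test in both branches raises the chance of any false positive to about 9.8%.

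**The 390.** It takes 15% of all 2,600, although tumour donation is optional (9.2.1) and testing is limited to those who consent (9.2.2). Section 1.2.1 gives prevalence as 15–20%. With 80% availability (an assumption; the protocol gives no figure), 2,600 × 0.80 = 2,080 have a result, so 312 to 416 are mutated. Scaling the mutated events in proportion, power at the stated HRs is 79–83% with 312 and 91–92% with 416.

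**The case against.** Several points on the other side stand.

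- **No conclusion is written in.** A reader might infer that the plan declares aspirin effective only without the mutation. It does not. Section 10.3.3 fixes tests and levels, not a rule for reading their pattern. The risk is misreading.
- **The result depends on the scenario.** Non-mutated only is the commonest pattern when the primary is significant and a common effect is near the target. At HR 0.70 it is not.
- **The plan is not blind to the effect it looks for.** With HR 0.50 in mutated and 1.00 in non-mutated patients, it detects the mutated effect in about 85% of trials. The 1% branch has about 81% power given a negative primary. Non-mutated only then occurs in roughly 0.1% of trials or fewer.
- **Non-mutated patients are not unexamined in the negative branch.** They form 85% of the non-significant primary. That is still no separate estimate.
- **The error statement is sound**, and an unbudgeted 5% interaction test would breach it.
- **The 390 cannot be called wrong.** The range of 312 to 416 brackets it.

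It can also be said that the analysis plan, not at hand, may add an interaction estimate. It may, but the protocol itself sets the tests, levels, branching and power, and presents them as the formal test of this hypothesis. The objection narrows the point without removing it.

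**Conclusion.** The point holds in this form: the protocol promises a formal test of a difference in effect and fixes tests that cannot provide one. At the design effect, with a significant primary and 15% prevalence, a uniform benefit would appear significant in non-mutated patients only in about 65% of trials, falling to about 50% at a common HR of 0.70. These figures assume proportional hazards, events split in proportion to prevalence, and a mutation result for every participant.

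The documents do not support the stronger readings that the plan states a false conclusion, would usually miss a large mutated-only effect, or misstates its type I error. The tissue question justifies showing a range, not a single corrected number.

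**What to change.** In 10.3.3, name the treatment-by-PIK3CA interaction as the assessment of the differential-effect hypothesis: the ratio of HRs with its 95% CI, with both subgroup HRs and CIs reported whether or not the primary is significant. Keep the Holm and 1% tests, described as tests of effect within a subgroup. If another method replaces the logrank test, as 10.3.1 allows, form the contrast on the effect measure then adopted.

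State that the interaction sits outside the 6% error statement, or restate that bound: a two-sided 5% interaction test takes the any-false-positive risk to about 10%. State its power in 10.4.6.A: about 85–90% for HR 0.54 vs 1.00 and about 50% for 0.54 vs 0.80.

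Optionally, note in 10.4.6.A that 390 presumes a result for every participant, and give detectable HRs over a range such as 312 to 416 mutated patients, with the availability assumption stated.

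The cost is protocol and analysis-plan wording and one model term. No extra patients or samples are needed.

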# **10.4 SAMPLE SIZE AND POWER**

In calculating an appropriate sample size for the trial, each cohort is considered separately in order to 1) account for the differences in disease behaviour and recruitment between tumour sites observed in previous studies and 2) ensure that the individual cohort-specific comparisons are adequately powered. Additionally, within the prostate cohort, the radiotherapy and prostatectomy groups are separately powered.

In the combined analysis, as well as for the cohort-specific analyses, the primary comparison will be aspirin vs. placebo (with the two aspirin arms combined). Each individual cohort is sized under the proportional hazards assumption to ensure adequate power using the logrank test to demonstrate effects of aspirin (specified as target hazard ratios) on the primary outcome measures. Power is set at 90% with the exception of the gastro-oesophageal cohort which has 80% power. The target effect sizes are of a similar magnitude across the four cohorts and represent realistic effect sizes, similar to those seen for a range of adjuvant therapies across cohorts. They may be smaller than target effect sizes in some adjuvant trials where potential benefits are balanced against higher costs and greater toxicity of the experimental therapy.

For each cohort-specific comparison, analyses are planned for 5-6 years after recruitment of the last participant to that cohort, but the exact timing will be based on the number of outcome events that have been observed in the control arm, and this will be monitored throughout the trial. The sample sizes needed to observe the required number of events are estimated based on anticipated recruitment rates (informed by recruitment rates in previous similar trials and a feasibility survey of participating Investigators), including allowance for slower accrual during the earlier stages of the study, and a small percentage of participants having incomplete follow-up data on the outcome of interest. The total sample size across four cohorts combined will be approximately 9,920 participants. In order to reach the target number of randomisations, we anticipate registering at least 11,000 participants for the run-in period (assuming at least 10% drop-out following the run-in).

As noted above, in addition to the main sample size calculations, for each cohort, the power of the logrank test with the calculated sample size and assuming a delayed effect of aspirin emerging after the first 2 years is also indicated.

# 10.4.1 BREAST COHORT

In the breast cohort, based on data from recent trials of adjuvant chemotherapy in similar breast cancer cohorts (specifically TACT, BIG 02-98 and GEICAM), as well as results from the recent Indian study of pre-operative progesterone, and additionally considering that a gradual improvement has been observed over time in outcomes for these patients, 5-year IDFS in the control group is expected to be approximately 80%. The number of patients for this cohort is designed to have 90% power at a 5% 2-sided significance level to demonstrate a 4% absolute improvement in this rate at 5 years (corresponding to hazard ratio, HR=0.78).

Assuming proportional hazards, this will require 275 control arm IDFS events (717 events in total) to be observed. Assuming that the cohort takes  $3^{1}/_{2}$  years to recruit, with the analysis taking place 6 years after the last randomisation, and that complete primary outcome data will not be obtainable for 10% of randomised participants by the time of analysis, the anticipated sample size needed to observe this number of events is approximately 3100 randomised participants. We expect to register at least 3450 breast cancer participants for the run-in period to allow for at least 10% not proceeding beyond that stage.

If an effect of aspirin were not observed for the first two years, it is estimated that the power achieved by the logrank test at the time of analysis would be approximately 83% with the proposed sample size. This calculation assumes a hazard ratio of 1 (no effect) over the first two years followed by a hazard ratio of 0.71 thereafter, which yields a mean hazard ratio of approximately 0.78 (the targeted hazard ratio for this cohort) at the time of the primary analysis of the cohort.

# 10.4.2 COLORECTAL COHORT

In the colorectal cohort, based on data from recent trials of adjuvant chemotherapy regimens in similar cohorts of colorectal cancer patients (specifically MOSAIC and QUASAR^109), and also considering that the Add-Aspirin cohort will be more mixed (including patients who haven't had chemotherapy and older patients), 5-year DFS in the control group is expected to be 70%. The cohort is designed to have 90% power at a 5% 2-sided significance level to demonstrate an absolute 5% improvement in this rate at 5 years (corresponding to HR=0.80).

Assuming proportional hazards, this will require 336 control arm DFS events (899 events in total) to be observed. Assuming that the cohort takes  $3^{1}/_{2}$  years to recruit, with the analysis taking place 6 years after the last randomisation, and that complete primary outcome data will not be obtainable for 10% of randomised participants by the time of analysis, the anticipated sample size needed to observe this number of events is approximately 2600 randomised participants. We expect to register at least 2890 colorectal cancer participants for the run-in period to allow for at least 10% not proceeding beyond that stage

If an effect of aspirin were not observed for the first two years, it is estimated that the power achieved by the logrank test at the time of analysis would be approximately 85% with the proposed sample size. This calculation assumes a hazard ratio of 1 (no effect) over the first two years followed

by a hazard ratio of 0.72 thereafter, which yields an estimated mean hazard ratio of 0.8 (the targeted hazard ratio for this cohort) at the time of the primary analysis of the cohort.

